with clear margins. Various outcomes from the examination and procedure can mean many patients are invited to reattend for a further colposcopy in a few weeks or months – such as follow up following a biopsy, unclear margins, mismatch between clinical findings and histopathological findings or the specimen being upgraded to a cancer. (5) Hence, colposcopy is often not a one stop clinic for service users so anxiety may be increasingly heightened as time progresses.

Despite colposcopy having undeniable significance in biological female's healthcare, the entire process is associated with high levels of stress and anxiety for patients. Colposcopy is a unique circumstance due to the intimate nature of the examination and the association with cancer. It is associated with fear, stress and loss of control. Many studies show that patients experience a "very high" level of anxiety when attending for colposcopy. (6) In comparison to other medical procedures, biological female patients experience a higher level of anxiety when attending colposcopy than when they are attending for cardiac surgery. (6,7) Anxiety can negatively impact a person's cognitive abilities and decreases the ability to recall and act on advice, leading to patients being less likely to comply with any information given. (8) Higher pre-procedural anxiety is predictive of post operative pain reported by patients in gynecological settings. Thus, by addressing these feelings, clinicians can reduce pain perception, however reducing this during a procedure without pharmacological agents remains a difficult task. (9)

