There are multifaceted benefits from using VR as a form of digital distraction. Firstly, it is nonpharmacological. This circumvents potential side effects associated with sedatives or anxiolytic medications. (20) Secondly, its versatility allows tailoring of experiences to individual preferences, accommodating various ages groups and clinical scenarios. Moreover, the interactive and customisable nature of VR allows healthcare workers to engage patients in the decision-making process, fostering a collaborative approach. (21) Ambulatory procedures should use multimodal forms of pain relief including pharmacological as well as non-pharmacological. By giving the patient options, this will increase the number of successful procedures. (22)

A 2023 systematic review looking at the use of VR in pain management shows it as a feasible option, with a reduction in pain perceived and anxiety levels in surgical patients. (23) Other recent studies in gynecological outpatient settings such as brachytherapy rod removal have shown it to be an effective adjunct to improve pain and anxiety score with a similar efficacy to nitrous oxide. (20) Moreover, it has also been shown to increase emotional detachment from the procedure in patients, aiding relaxation, reducing unnecessary movement and allowing the healthcare professionals to focus on the treatment. (24) This dual effect should both increase clinic efficiency as well as decrease the frequency of procedure abandonment. The use of virtual reality during colposcopy procedures has not yet been published, therefore, it is important to establish if this improves patient anxiety, pain and overall satisfaction.

Patient and Public Involvement

A scoping exercise was carried out in the outpatient colposcopy clinic prior to initiation of the intervention to assess the people attending attitudes in relation to colposcopy and the introduction of VR headsets. Biological females attending clinic were interviewed by the lead researcher and given questionnaires to assess their attitudes to colposcopy and acceptability of using the headset. Most participants reported feeling "nervous" and "jittery" as "very much so," on the modified STAI

score. 87% of participants interviewed (N=15) stated they would be accepting to use the VR headset during their consultation and thought it would be of benefit.

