- Understanding the acceptability and effectiveness regarding anxiety reduction of VR interventions within the procedural groups and how these might vary as a function of different patient demographics.
- Feasibility and acceptance of intervention from clinicians' perspective
- To investigate if the introduction of VR have an impact on patients' attendance to follow up appointments

Study Design

Trial design

The “Mind over Cervix” trial is designed as a single centre, prospective, non-blinded, randomised control trial with two parallel groups to determine the superiority of VR headsets in patients’ anxiety reduction and pain reduction during outpatient colposcopy compared to standard care.

Study setting

The study will be carried out in the colposcopy outpatient clinic in Queen Elizabeth Hospital (QE), Gateshead, Gateshead Health Trust.

QE is a large tertiary referral centre for gynaecology and colposcopy in the north-east of England. Over 1700 patients attend the department for colposcopy annually. (24) Colposcopy is provided by consultant gynaecologists, consultant gynaecologists and nurse colposcopists.

Withdrawal Criteria

Patients can withdraw from the study at any time and without giving a reason. Deciding to withdraw or not take part in the study will not have any effect on the standard of care they receive. In addition, any staff member may withdraw their consent at any time without giving a reason.

Recruitment

Queen Elizabeth Hospital in Gateshead is a large tertiary referral centre for Gynaecology and colposcopy in the northeast of England. Over 1700 patients attend the department for colposcopy annually. (24)

Following prospective ethical and trust approval via IRAS, all patients who attend for outpatient colposcopy will be informed of the study prior to their arrival to the department. They will be sent a patient invitation leaflet (Appendix 1) to their home through the post 2-4 weeks prior to their appointment to inform them of the study and the fact they may be approached. On arrival to the department, a poster will be displayed in the department to remind attendees of the study and the potential for their participation (Appendix 1a). They will be given information again via the PIL (Appendix 1b) which will be provided by the clerical staff when they attend reception to check in for their appointment.

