All clinicians and clinic staff who will be involved in application of the headset to participants have had training from Rescape or PI on how to use to the system. The training video is available to all staff if they feel they need to renew their training. The training log has been recorded and will be added to the standard operating procedure file. (SOP).

Criteria for discontinuing or modifying allocated interventions

Participants are free to remove the VR headset at any point in the intervention. They will be informed of this prior to its application. Participants will be free withdraw consent and leave the trial at any point during the process. They do not have to give prior warning or any explanation. This will not change the clinical procedure being conducted. If participant becomes upset or display signs of anxiety during the procedure the distress protocol will be followed (Appendix 3)

There is a risk of cybersickness during the application of the headset. Patients will be informed of this during the consent process and informed to remove the headset should this occur. This is included in the distress protocol and the deviation log (Appendix 7).

Strategies to improve adherence to interventions

Potential participants will be shown photographs of the VR headset prior to enrolment in the trial via the PIL provided to ensure understanding of its involvement. If they are in the VR intervention arm, they will be given the opportunity to see the VR device prior to beginning the therapy. They will be given the opportunity to try the headset on prior to beginning the colposcopy consultation to ensure they are amenable to having it placed prior to the procedure.

Relevant concomitant care permitted or prohibited during the trial

Some patients attending colposcopy will only have an inspection performed of the cervix, other patients will have a biopsy or a LLETZ procedure performed. If a biopsy or LLETZ procedure is performed, the entire colposcopy experience will take longer and may be more painful than if only inspection is performed. If a patient needs a biopsy or LLETZ performed, this will not be known until the colposcopy inspection

has taken place, so it is not possible to stratify the study group arms prior to enrolment in the trial.

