Participants will complete a questionnaire (Appendix 6a) with STAI questions prior to randomisation to get a baseline anxiety level. This will be compared to the post procedural questionnaire (Appendix 6b) with the same questions to compare the actual anxiety levels during the procedure. Comparison will be made between the two arms.

Secondary Outcome

Pain reduction: Pain scores will be measured by a Numeric Rating Scale (NRS) from 0 through to 10. 0 represents “no pain” and 10 represents “worst pain imaginable”. This will be shown alongside a visual analogue scale (VAS) of pain on animated faces. This is a validated measure for pain, is easy to use, has high compliance rates and detects meaningful change. (29,30,31) Participants will be asked to state the “maximum pain felt, if only for one moment,” and also state the “average pain experienced,” throughout the procedure. Respondents will select the single number that best represents their pain intensity. Results from participants in the intervention arm will be compared to participants in the control arm.

Understanding the acceptability and effectiveness of VR in variations of patient demographics: Participants will be asked to state the following demographics – age, ethnicity, parity, menopausal status, previous attendances to colposcopy and previous treatments in colposcopy. Acceptability will be monitored by participants ongoing consent of using the VR headset. If a patient removes the headset before the colposcopy assessment is completed, this will be noted in the post procedural questionnaire and be noted that the patient did not find it acceptable. The demographics of this patient cohort will be reviewed to see how VR effects different patient demographics.

Feasibility and acceptance of intervention from clinicians’ perspective: Following completion of the colposcopy assessment, the clinician will be asked to complete a short survey of their experience using VR. (Appendix 6c) These will be questions on a Likert scale from “strongly disagree” to “strongly agree”. Clinicians will be asked did they find it easy to use the VR in their clinic, did they find it beneficial to the consultation, did they find it easy to communicate with the patient during the consultation.

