Does the introduction of VR have an impact on patients attendance to follow up appointments: Following completion of the trial intervention period, a retrospective analysis of patients who are enrolled in the trial and require a further attendance, adherence to their follow-up appointments will be monitored. This will be completed using the department’s electronic booking system to monitor attendance. This will be compared to the department’s previous 6-month non-attendance. Data will be compared to see if enrolment on the trial and the addition of VR had any benefit in patient compliance to follow-up.

Plans to promote participant retention and complete follow-up

Participants are free to withdraw from the trial at any stage without explanation. This will be explained to them.

As participation in the trial is a relatively short amount of time, lasting only as long as their clinic appointment, we do not anticipate retention and follow-up being a significant factor in our study.

Data management

Research team members CMcF, NR, WM and LP have longstanding experience with data collection and storage. All study records and the Investigator Site File will be kept at site in a locked filing cabinet with restricted access. The Trial Master File will be held at Queen Elizabeth Hospital, Gateshead NHS trust in a locked filing cabinet with restricted access.

Data linkage will require use of NHS number which will be done securely with the IT network of Gateshead NHS Trust by a researcher with an NHS contract. The identifiable data will be stored with access restricted to the research team and will be protected by passwords. Computers will be protected by passwords and stored securely. The research team will follow guidance to ensure that personal data cannot be seen on screens or any other media by those outside the research team. Documentation including personal data will be minimal and if possible avoided and will be stored in locked cabinets in locked offices and destroyed in line with confidentiality requirements of the Trust as soon as it is no longer needed.

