Demographic characteristics will be explored for missing data and distribution abnormalities. Means and standard deviations will be used to characterise the sample. Analysis of covariance (ANCOVA) and non-parametric tests (Mann – Whitney) will be used to determine whether the VR intervention lead to a significant difference between baseline and follow up anxiety between control VR and control arm. Descriptive statistics (i.e. age, gender, ethnicity, previous attendance to colposcopy, menopausal status and parity) for the baseline values will be presented within each randomized controlled arm. P values will be used to estimate statistical significance for all analysis.

End of Study Definition

The end of study will be upon completion of the final visit of the last participant/volunteer enrolled in the trial.

Project Management Plan

PROJECT MANAGEMENT PLAN (with project milestones)			
Action	Timescale	Responsibility	Indicator / Outcome / Evidence
Develop protocol	Aug 23- Dec 23	Fellow and Supervisors	Creation of protocol to ensure robust methodology and outcome measures
Scoping exercise amongst service users	Oct 23- Dec 23	Fellow	Ensure in keeping with service users focus
Train staff on VR equipment	Oct 23 - ongoing	Fellow, Rescape	Train staff alongside Rescape to use equipment
Recruitment PPI work for patient information leaflets, questionnaires	Oct 23 - ongoing	Fellow, Research nurses	Approaching service users for feedback to ensure legibility
Begin recruitment of service users	March 24 – August 24	Fellow, Research nurses	Consenting and awareness
Begin trial and data collection	March 24 – August 24	Fellow, Research team, supervisors	Comparison of VR to standard care
Completion of data collection and writing up	Aug 24 – Dec 24	Fellow, Supervisors	Writing up analysis
Dissemination of information	Jan 25 – Aug 25	Fellow, supervisors	Conference presentations, publications

Oversight and monitoring

Composition of the coordinating centre

[name] (Principal investigator) *Clinical Research Fellow Gynaecological Oncology*

- Design and conduct of “Mind over Cervix”.
- Preparation of protocol and revisions
- Chair of steering group

- Overall responsibility for study milestones
- Preparation of case report forms (CRFs)
- Managing, monitoring and ensuring integrity of collaborative relationships

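### Follow-up attendance is compared only with the department's previous six months; no VR-versus-control comparison is specified, so the stated contrast does not isolate the effect of VR

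*Combined protocol and SAP*

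**What the plan says.** The objective is set out under Secondary objectives: "To investigate if the introduction of VR have an impact on" attendance at follow-up appointments. The summary table at the front and the Outcomes section repeat the question. None of the three names a comparator.

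The method appears once, at the end of Plans for assessment and collection of outcomes. It is "a retrospective analysis of patients who are enrolled in the trial and require a further attendance", with attendance read from the electronic booking system. The comparator is the department's "previous 6-month non-attendance. Data will be compared to see if enrolment on the trial and the addition of VR had any benefit" in compliance with follow-up. Arms are not mentioned.

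The same section treats the other outcomes differently. For anxiety it says that the two arms will be compared. For pain it says: "Results from participants in the intervention arm will be compared to participants in the control arm". Statistical methods names ANCOVA and Mann-Whitney for anxiety and gives no method for attendance, though it applies P values to all analyses. The Project Management Plan has the entry "Comparison of VR to standard care" but ties it to no outcome.

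**The concern.** The question is whether VR changes attendance, and the trial has a concurrent randomised control group that could answer it. The stated contrast does not use that group as the comparator. It sets people who attended an index visit and consented to a trial against a departmental figure from an earlier period. How that figure is built is not stated. If it includes first appointments, the two populations differ further, because every enrolled patient has already attended once.

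Two errors are possible. The trial could report a benefit of VR that is really selection or calendar time. Or, if the arms are pooled, it could understate a real benefit, because about half the enrolled patients never had the headset during the procedure. Attendance is listed among the key secondary outcomes, so a claim about it is likely to be reported.

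**Working it through.** **Plan's own figures.** The only sample size is for the main comparison. A two-sided two-sample t-test with d = 0.5, alpha 0.05 and power 0.8 needs 63.77, so 64 per arm and 128 in total; 128 × 1.1 = 140.8, so 141. This reproduces, but it says nothing about attendance. The documents give no non-attendance rate, no share needing follow-up and no attendance test, so every rate below is assumed.

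**What the stated contrast measures.** Let H be the historical non-attendance rate, C the control-arm rate and V the VR-arm rate. Pooling the arms 1:1, the contrast is H − (C + V)/2; the effect of VR is C − V.

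- Selection or calendar time worth 5 points, no VR effect: H = 20%, C = V = 15%. Stated contrast 20 − 15 = 5 points; VR effect 0.
- No selection, VR halves non-attendance: H = C = 20%, V = 10%. Stated contrast 20 − (20 + 10)/2 = 5 points; VR effect 10.
- VR arm alone against history, with selection and VR each worth 5 points: H = 20%, C = 15%, V = 10%. Contrast 10 points; VR effect 5.

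The first two cases give the same 5-point result, one with no VR effect and one with a large effect.

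**False findings of benefit against history.** Method: exact binomial enumeration of the pooled two-proportion z-test at two-sided 5%, counting rejections in the direction of benefit, with no VR effect. Assumed: 850 historical patients (half of the 1,700 or more a year in Study setting, which counts attenders) and 40 or 70 enrolled patients needing follow-up.

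| Enrolled v historical non-attendance | 40 enrolled | 70 enrolled |
|---|---|---|
| no gap (10%, 15% or 20% in both) | 1.3-1.8% | 1.6-2.1% |
| 10% v 15% | 9.0% | 17.0% |
| 15% v 20% | 8.9% | 15.0% |
| 10% v 20% | 32.0% | 56.3% |
| 5% v 15% | 41.1% | 71.4% |

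With 400 or 1,200 historical patients, the 5-point rows stay at 8.6-9.2% and 14.1-17.4%.

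**The arm comparison, same test.** With 20 or 35 per arm, non-attendance of 10-20% and the same mix of patients in both arms:

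- Two-sided type I error is 3.9-5.0% with 20 per arm and 4.9-5.7% with 35.
- The 95% half-width, 1.96 × √(2p(1 − p)/n), is 18.6-24.8 points with 20 per arm and 14.1-18.7 with 35.
- The probability of detecting a halving, in the direction of benefit, is 5.2-13.6% with 20 per arm and 12.4-21.8% with 35.

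**If VR changes who needs follow-up.** This need is settled after randomisation. Background and rationale says: "Various outcomes from the examination and procedure can mean many patients are invited to reattend for a further colposcopy". The section on concomitant care says: "If a patient needs a biopsy or LLETZ performed, this will not be known until the colposcopy inspection" is done. The protocol also expects of VR: "This dual effect should both increase clinic efficiency as well as decrease the frequency of procedure abandonment". Suppose VR has no effect on attendance, low-risk patients miss 10% of appointments and high-risk patients 20% or 30%, and the high-risk share is 50% in control but 40% or 30% in VR. The spurious differences are 15% v 14%, 15% v 13%, 20% v 18% and 20% v 16%, that is 1 to 4 points. Two-sided error is 5.0-6.2% with 20 per arm and 5.4-7.1% with 35.

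**The case against.** The strongest reply is that this is loose drafting. The method's last sentence names both enrolment and the addition of VR; only the second differs between arms, and comparing arms is the natural way to separate them in a two-arm randomised trial. That reading is possible. But the sentence states a purpose and names no second comparator, while anxiety and pain each get an explicit arm comparison. Pooling remains an inference, and so does the halving that depends on it.

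A second reply is that the objective concerns the introduction of VR, for which a departmental before-and-after rate is relevant, and that controls are offered a headset once their participation ends (Intervention description), so an unexposed reference has some value. This supports keeping the historical rate as context. It does not let that rate separate VR from consent selection or calendar time.

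Third, this is an unpowered secondary outcome, and the arm comparison would be imprecise. That is true, and it is why the result should be labelled exploratory; it is no reason to rely on a contrast that cannot answer the question.

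Fourth, the illustration has no documentary inputs, and the direction of the patient-mix shift is a guess. Background and rationale says that patients whose procedure cannot be completed often go to a theatre list, which could push the mix the other way. Both points stand. The figures show a mechanism, and the conclusion does not depend on them.

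**Conclusion.** The concern holds. The only comparator stated for follow-up attendance is historical, and followed as written it mixes any effect of VR with consent selection and calendar time. If the departmental figure includes first visits, it also mixes in selection of attenders.

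The size cannot be fixed from the documents. Under the assumed rates, the chance of a false benefit runs from about 9% to 17% for a 5-point gap and from 32% to 71% for a 10-point gap, against 1-2% with no gap. The halving of a true effect rests on two further assumptions: that the arms are pooled and that controls match the historical rate.

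This should be fixed before analysis. It concerns one secondary outcome and leaves the anxiety and pain comparisons untouched.

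**What to change.** State in the attendance paragraph and in Statistical methods that:

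- the main attendance comparison is VR versus control, by randomised arm;
- the outcome is attendance at the first booked follow-up appointment, within one window common to both arms;
- the result is a risk difference with a 95% confidence interval, labelled exploratory;
- the departmental six-month rate is descriptive context only, with a statement of which appointments it covers;
- the number and proportion needing follow-up are reported in each arm, and the comparison is described as fully protected by randomisation only if VR does not affect who needs follow-up.

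The cost is about a paragraph of text and one count per arm. No new data source is needed: the booking-system review already covers enrolled patients, and the log described under Confidentiality allows linkage to study data.

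The limits should be written down too. At most about 70 per arm (141/2) can contribute, and only those needing follow-up will. With 20-35 per arm the half-width is about 14-25 points and power for a halving about 5-22%, so a null result would not rule out an effect. The headset offer to controls may dilute any difference. The window also has to fit the timetable: the protocol puts further visits weeks or months later, while data collection ends in August 24 and writing up in December 24, so a long window could leave out late recruits.
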